6.2.6 Antibiotic Treatments and Concomitant Medications

Concomitant medications taken three months prior to study start will be coded using the WHODRUG dictionary, Version B2 201609 or later, and the number and percentage of patients will be summarized in tables. Antibiotic usage during the study will also be coded using the WHODRUG dictionary, Version B2 201609 or later, and summarized in tables. The most current WHODRUG dictionary will be used at the time of analysis. These prior non-antibiotic medications used for chronic conditions will be reported in listings, including the medication name (coded), reason for prescription, route, and start date and end date. All medications will be summarized using descriptive statistics by the pre-period and post-period for the FAS population. For post-period patients, discharge to complete care in an outpatient setting on the same day Dalvance was provided and reasons for not being discharged to an outpatient setting will be summarized by patient counts and percentages.

6.2.7 Safety Assessments

The reporting period for adverse events (AEs) begins from the time of the signing of the Patient Authorization throughout the patient's enrollment in the study. AE information will be collected in an ongoing fashion through patient reporting AEs to their healthcare provider.

All AEs will be coded and summarized by the pre-period and post-period for the FAS population by system organ class and preferred term based on the MedDRA coding dictionary Version 20.0 or later; the most current MedDRA coding dictionary will be used at the time of analysis. AEs will be summarized as related to treatment if there is evidence to suggest a causal relationship between the study drug (any antibiotic given for ABSSSI from enrollment, including the pre-period or post-period) and adverse event, and as not related if there is no evidence to suggest a causal relationship between the study drug and adverse event. For severity, the most severe case of an AE by a patient will be reported, with order of most severity as: Severe>Moderate>Mild.

A listing of adverse events will also be given for each patient and will include the reported term, seriousness, severity, relationship to treatment, action taken with medication, event outcome, and date for each event reported.

6.2.8 Laboratory and Microbiology

All laboratory and microbiological assessments will be summarized for baseline and follow-up visit in tables with descriptive statistics by the pre-period and post-period for the FAS population. Laboratory results will be reported for the scheduled baseline and day 10-14 visit. The first microbiology result for each patient at baseline and follow-up, respectively, will be summarized for each time period. Where more than one unit is collected within analysis, values will be converted to a common unit and displayed for analysis. Laboratory conversions to standard international units are reported in the table below:

Laboratory Unit	Standard International Unit	Factor
Sodium mEq/L	Sodium mmol/L	x1
Potassium mEq/L	Potassium mmol/L	x1
Bicarbonate mEq/L	Bicarbonate mmol/L	X1

A listing of laboratory and microbiological assessments will also be given for each patient and will include the time period the assessment was taken (e.g., initial care, follow-up), date of assessment, laboratory test, reported laboratory value, reported laboratory unit, specimen type, method of collection, if any isolated were grown from the specimen, the organism grown, if this organism was tested for susceptibility, what antibiotics were used for susceptibility, the level of susceptibility (sensitive, resistant, intermediate, indeterminate) and the minimum inhibitory concentration (MIC) with corresponding unit.

6.2.9 Healthcare Costs

Total costs of care for each study patient over the 44-day period of interest will be estimated by multiplying estimates of utilization of healthcare services collected during the conduct of this study by corresponding unit costs. Unit

costs will include: cost of day in hospital, cost of day in ICU, ED visit, healthcare visits, surgical procedures, imaging tests, catheter placement (PICC line/central line) and microbial culture. Further detail is given in Section 4.5 of this document.

Summary statistics for total costs of care will be estimated for the pre- and post-periods for the FAS population.

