1.2 Purpose

In addition to a lack of clinical guidelines or critical pathways to inform treatment of ABSSSI patients, many contributing factors are responsible for continuing to admit ABSSSI patients to receive IV antibiotic therapy, who could otherwise be treated in an outpatient healthcare setting. First, physicians may not have experience with or training for use of newer IV antibiotics, including use of long-acting IV antibiotics. Information on use of long-acting IV antibiotics may be limited to clinical trials, which test agents in highly selected populations under optimized settings with limited “real-world” generalizability. Second, physicians may have safety concerns related to adequate patient follow-up with the use of long-acting IV antibiotics. Third, there may be barriers to provision of OPAT, including institutional time spent coordinating care and insurance-related barriers.

A new study is therefore required to better understand the “real-world” effectiveness of a new critical pathway that includes use of a long-acting antibiotic for the treatment of ABSSSI. In addition to tangible economic benefits associated with reducing unnecessary admissions, implementation of a new critical pathway may reduce utilization of healthcare services in the inpatient and outpatient care setting, increase patient satisfaction, improve patient health-related quality of life (HRQoL), and reduce patient productivity loss/absenteeism.

2 Study objectives

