3.2.2 Post-period

During the post-period, all enrolled subjects will receive treatment for ABSSSI with dalbavancin at each participating site. Dalbavancin will be administered as a single IV dose of 1500 mg over 30 minutes (1125 mg over 30 minutes if CrCl <30 mL/min, for those not on regularly scheduled dialysis).¹² Dalbavancin will be provided to sites by study sponsor.

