6.1 Cost

Cost data will not be collected in the study. As these data often vary by site and insurer, representative unit cost estimates for each healthcare service/medication identified during the collection of outcome measures will be identified. Total costs of care for each study subject will then be estimated by multiplying utilization of healthcare services collected via the CRF by the corresponding unit costs; mean/median total costs of care during the pre- and post-periods will then be estimated and compared. The approach to the pre-post comparison and unit costs will be defined in the SAP.

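### The unit-cost list in SAP 6.2.9 names no drug although Protocol 6.1 calls for medication unit costs, so the cost total may omit the antibiotic cost difference between periods, with unknown direction and size

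*SAP*

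**What the plan says.** Protocol 6.1 states that cost data will not be collected in the study. Instead, "representative unit cost estimates for each healthcare service/medication identified during the collection of outcome measures will be identified". Each patient's total is then obtained by "multiplying utilization of healthcare services collected via the CRF by the corresponding unit costs", and the two periods are compared on mean or median total cost. The details are delegated: "The approach to the pre-post comparison and unit costs will be defined in the SAP".

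SAP 6.2.9 takes up that task. It builds the 44-day total from utilization and unit costs, and it lists the unit costs: "costs will include: cost of day in hospital, cost of day in ICU, ED visit, healthcare visits, surgical procedures, imaging tests, catheter placement". After line placement, the only item left in the list is microbial culture. The section then adds: "Further detail is given in Section 4.5 of this document". Sections 4.4 and 4.5 are not in the supplied text. The output is Table 22, with summary statistics by period for the full analysis set.

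Three other places bear on the point:

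- Protocol 3.2.2: "Dalbavancin will be provided to sites by study sponsor".
- SAP 5.0, on changes from the protocol analyses, covers dropped laboratory derivations and changed tests. Its visible text does not mention costs.
- SAP 6.2.6, Table 6 and Listing 6 show that antibiotic use during the study is coded, tabulated and listed.

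**The concern.** The protocol names medication as something to be priced. The SAP list goes into enough detail to price a culture, yet it has no drug item. What separates the two periods is the antibiotic: investigator's choice before, dalbavancin after. A result labelled as a total cost that follows this list would count the hospital days, line placements and visits that the pathway may change, but not the treatment that was exchanged.

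The protocol gives economic benefit as part of the motivation (Protocol 1.2: "In addition to tangible economic benefits associated with reducing unnecessary admissions"), so readers are likely to take Table 22 as the economic result. Because the sponsor supplies dalbavancin, the hospital need not incur a purchase cost for it. It will therefore be counted only if the plan assigns it a price.

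**Working it through.** The documents contain no unit cost, drug price or cost result, so there is no stated figure to reproduce. The check is a comparison of the two texts, followed by algebra for the omitted term.

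**Comparison of the texts**

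| Item | Protocol 6.1 | SAP 6.2.9, visible list |
|---|---|---|
| Hospital and ICU days | covered as services | named |
| ED and other healthcare visits | covered as services | named |
| Surgery, imaging, line placement, culture | covered as services | named |
| Antibiotics and other medication | named | not named |
| Further detail | left to the SAP | left to Section 4.5 (not supplied) |

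**The omitted term**

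Inputs:
- Planned reduction in hospital stay: 2 days (Protocol 6.3; SAP 6.1.2).
- H = cost of one hospital day. Not in the documents.
- D = mean antibiotic cost per post-period patient. Not in the documents.
- U = mean antibiotic cost per pre-period patient. Not in the documents.

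Assume that the 2-day reduction occurs, that all other use is equal, and that H contains no drug cost.

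- Saving by the visible list: 2 × H = 2H. D and U do not enter.
- Saving with drugs priced: 2H − (D − U).
- Error from the omission: 2H − [2H − (D − U)] = D − U.
- The sign of the cost result changes where 2H − (D − U) = 0, that is, at D − U = 2H.

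Assumed range for D − U, taken on both sides of zero because the documents do not fix its sign:

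| D − U (assumed) | List gives | With drugs priced | Omission |
|---|---|---|---|
| −0.5H | 2H | 2.5H | understates the saving |
| 0 | 2H | 2H | no effect |
| 0.5H | 2H | 1.5H | overstates the saving |
| H | 2H | H | overstates it twofold |
| 2H | 2H | 0 | reports a saving where there is none |
| 3H | 2H | −H | reports a saving where there is a loss |

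**If the hospital-day cost already contains drugs**

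The SAP does not say whether it does. Let b be the antibiotic part of H. Pricing antibiotics separately then requires a day cost of H − b, and the saving is 2(H − b) − (D − U). If antibiotic prices are added without removing b, the result is 2H − (D − U), which is too large by 2b. Adding drug prices is therefore not enough. The content of the day cost must be stated as well.

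**The case against.** The strongest reply is that SAP 6.2.9 does not claim to be complete. It sends the reader to Section 4.5, and text absent from the supplied copy cannot be treated as absent from the plan. Section 4.5 may price every antibiotic, and a statement of what the costs will include need not be exhaustive. This stands, and it makes the conclusion conditional. It does not remove the mismatch between the protocol and the visible list. If Section 4.5 does price drugs, 6.2.9 should say so.

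Second, the protocol's calculation sentence speaks only of services, and the protocol leaves unit costs to the SAP. A SAP that defines them is doing what it was told, so silence in SAP 5.0 does not prove an undisclosed change. This stands in part. However, the unit costs in that calculation are most naturally the ones the preceding sentence describes, and that sentence names medication.

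Third, a reader might infer that dalbavancin is costed at zero. The documents do not say this. They say who supplies it, and the protocol relies on representative unit costs, so free supply does not imply a zero price.

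Fourth, a reader might infer that the comparison is tilted toward the pathway. The documents do not support that either. If the list is complete, usual-care antibiotics are unpriced too, the omitted quantity is D − U, and no price is given to settle its sign.

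Finally, cost is not a listed primary or secondary outcome, and 6.2.9 plans only summary statistics. That limits the importance of the point.

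**Conclusion.** The point holds as an inconsistency with a conditional consequence. Protocol 6.1 calls for medication unit costs, the list in SAP 6.2.9 names none, and the visible text of SAP 5.0 records no departure. Unless Section 4.5 supplies drug prices, the cost total is wrong by D − U per patient, and under the planned 2-day reduction it would change sign at D − U = 2H. This rests on the assumptions stated in the working: other use equal, the planned reduction realised, and no drug cost inside H.

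Neither the direction nor the size of the error can be determined from the documents. It is also too strong to infer that a saving would be reported regardless, because the list-based result still depends on observed stays, readmissions, ICU days, visits and surgery. Nor does it follow that the trial cannot address cost at all: antibiotic use is recorded, so the drug component can be added. The mismatch itself is clear from the text. The size of its effect is not, and the primary comparison of hospital days is untouched.

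**What to change.** In SAP 6.2.9:

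- Name a representative unit cost for every antibiotic given for the ABSSSI in both periods, with a non-zero representative price for sponsor-supplied dalbavancin.
- State whether the hospital-day cost already includes inpatient drugs and, if it does, how double counting is avoided.
- Make this consistent with Section 4.5. If that section already prices antibiotics, a sentence in 6.2.9 saying so, together with the rule on the hospital-day cost, is enough.

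A separate item for outpatient administration does not appear necessary, provided the healthcare visits in the list include the infusion-centre and home-health visits that SAP 4.3 counts.

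If drug costs are excluded on purpose, record that in SAP 5.0 and label Table 22 as non-drug resource cost.

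The cost is some SAP wording and a few more unit prices. No new data collection is needed, because antibiotic use is already coded and listed (SAP 6.2.6, Table 6, Listing 6). The reported cost difference may become less favourable to the pathway.

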7.0 List of Potential Tables/Listings/Figures

Table shells are included in the document:

055123_ENHANCE_SAP_Table_Shells_DRAFT_v X.X_YYYYMMDD.docx.

§ Denotes output that can be produced at interim analysis. ¶ Denotes the minimum output necessary to support sample size confirmation. * Denotes output to be produced only for the sample size confirmation described in the protocol.

Table 1 Disposition of Study Patients : Enrolled Set§¶

Table 2 Patient Demographics at Baseline by All Patients: Enrolled Set§

Table 3 Comorbid Conditions Reported at Baseline: Full Analysis Set§

Table 4 Healthcare Resource Utilization at Previous 3 Months: Full Analysis Set§

Table 5.1 Infection Characteristics and Clinical Characteristics at Baseline: Full Analysis Set§

Table 5.2 Infection Characteristics and Clinical Characteristics at Day 10 to 14 Visit: Full Analysis Set§

Table 6 Use of Antibiotics by Patients During the Study: Full Analysis Set§

Table 7 Primary Outcome: Total Infection-Related LOS during Initial Care and Follow-up: Full Analysis Set§¶

Table 8 Secondary Outcomes by All Patients: Full Analysis Set§

Table 9 Secondary Outcome: Serious Adverse Events by SOC and PT: Full Analysis Set§

Table 10 Secondary Outcomes: Patient Satisfaction with Care: Full Analysis Set §

Table 11 Secondary Outcomes: Patient Work and Productivity Loss: Full Analysis Set§

Table 12 Secondary Outcomes: Patient Health-Related Quality of Life (SF-12): Full Analysis Set

Table 13 Other Outcomes: Full Analysis Set§

Table 14 Adverse Events- Overall Summary: Full Analysis Set§

Table 15 All Adverse Events by SOC and PT: Full Analysis Set§

Table 16 Adverse Events with Possible Causal Relationship to Study Drug by SOC and PT: Full Analysis Set§

Table 17 Adverse Events Leading to Study Discontinuation by SOC and PT: Full Analysis Set§

Table 18 Adverse Events Leading to Death by SOC and PT: Full Analysis Set§

Table 19 Laboratory Values: Full Analysis Set§

Table 20 Microbial Assessments: Full Analysis Set§

Table 21 Vital Signs: Full Analysis Set§

Table 22 Summary of Cost Analyses over 44 Day Period: Full Analysis Set

Table 23 Sample Size Confirmation^{¶*}

Figure 1 Box Plot of All-Cause Hospitalization Time During Initial Care and Follow-up for Patients Completing the Study by Pre- and Post-period: Full Analysis Set

Figure 2 Box Plot of Infection-Related Hospitalization Time During Initial Care and Follow-up for Patients Completing the Study by Pre- and Post-period: Full Analysis Set

[figure not shown]
Listing 1 Patient Disposition: Enrolled Set§¶

- Listing 2 Patients Who Did Not Meet Inclusion or Exclusion Criteria: Patients Excluded from Enrolled Set §
- Listing 3 Patient Demographics at Baseline: Enrolled Set§
- Listing 4.1 Medical History at Baseline Visit: Enrolled Set, Part 1§
- Listing 4.2 Medical History at Baseline Visit: Enrolled Set, Part 2§
- Listing 4.3 Medical History at Baseline Visit: Enrolled Set, Part 3§
- Listing 4.4 Medical History at Baseline Visit: Enrolled Set, Part 4§
- Listing 5.1 Infection Characteristics: Enrolled Set, Part 1§
- Listing 5.2 Infection Characteristics: Enrolled Set, Part 2§
- Listing 6 Antibiotic Usage: Enrolled Set §
- Listing 7 Prior Non-Antibiotic Usage for Chronic Conditions Reported at Baseline: Enrolled Set§
- Listing 8 Hospitalization, ED and Observation Unit Visits: Enrolled Set §
- Listing 9 Hospitalization Length of Stay: Enrolled Set §
- Listing 10 Other Healthcare Visits: Enrolled Set§
- Listing 11 SF-12 Questionnaire at Baseline and Day 14: Enrolled Set
- Listing 12 Patient Satisfaction Survey at Day 14: Enrolled Set
- Listing 13 WPAI at Day 14: Enrolled Set
- Listing 14 Surgical Interventions and Procedures: Enrolled Set§
- Listing 15 Adverse Events: Enrolled Set§
- Listing 16 Laboratory Results: Enrolled Set§
- Listing 17 Microbial Assessments: Enrolled Set§
- Listing 18 Vital Signs and Physical Examination at Follow-up: Enrolled Set§

9.0 Appendices

Appendix B: Derived Variables

[figure not shown]
Analysis Section (Visit)	Variable (Units)	Definition
General (Baseline)	Enrollment date	Informed consent date
General (Baseline)	Baseline date	Hospital admission date at initial episode of care
General (Initial Care)	Initial care indicator	If enrollment date \leq date \leq enrollment date + 13 days then = Yes Else = No
General (Follow-up)	Follow-up indicator	If enrollment date + 14 \leq date \leq enrollment date + 43 days then = Yes Else = No
Demographics (Baseline)	Age (years)	Round down to nearest integer((Initial hospital admission date - date of birth + 1)/365.25), when both dates are available.
Demographics (Baseline)	BMI	weight (kg)/ [height(m)] ² Where necessary, height and weight will be converted to proper units.
Infection Characteristics (Baseline)	CCI	Will be scored as described in Appendix C. Includes variables for raw score and 10 year survival probability.
Infection Characteristics (Baseline)	Immunocompromised	=YES if any of the following at baseline: 
 - Diabetes mellitus - Leukemia - Malignant lymphoma
Infection Characteristics (Baseline)	Fever	If temperature > 38 ° C then =Yes Else =No
Infection Characteristics (Baseline)	SIRS Criteria Met	SIRS criteria include abnormalities in temperature, heart rate, respiration, and white blood cell count. Specifically included are:

[figure not shown]
Analysis Section (Visit)	Variable (Units)	Definition
		
 • Fever of more than > 38.0°C or hypothermia with temperature < 36.0°C • Tachycardia with heart rate > 90 beats/minute or • Tachypnea with respiratory rate of > 20 breaths/minute or PaCO₂ of less than 32mmHg • Abnormal white blood cell count: leukocytosis >12,000/microliter, leucopenia <4,000/microliter, or >10% immature cells (bands).^{3,4} 
If 2 or more criteria present = Yes Else = No

Antibiotic Medications (Initial Care and Follow-up)	Days Received Antibiotic Medication	Σ (Medication end date – Medication start date +1), when both dates are available. If dates overlap (e.g., end date and next start date are identical) then subtract 1 from summation for each occurrence.
Primary and Secondary Outcomes (All visits)	Hospitalization LOS (days)	
For all-cause: Σ (Hospitalization end date – Hospitalization start date +1), when both dates are available. If ongoing at end of study or discontinuation date, use study completion date or discontinuation date as end date. For outcomes, LOS will be computed two ways: only inpatient hospitalizations visits and inpatient hospitalizations visits with prolonged observation status (e.g., time in observation status exceeds 1 day). For infection-related:

[figure not shown]
Analysis Section (Visit)	Variable (Units)	Definition
		Subset all-cause hospitalization time for patients with infection-related hospitalization stays
Primary and Secondary Outcomes (End of Study Visit)	Completers Flag	
If "Did the patient complete the study?" = 1 on the end of study visit CRF page and date of study completion does not equal missing, then =Yes, Else = No
 
This flag will be used to repeat certain primary and secondary outcomes that could be influenced by early discontinuation (e.g., LOS)

Secondary Outcomes (Follow-up)	Response to Therapy at End of Therapy Visit	
The response will be categorized as a "Complete Response" if at the day 10-14 visit there is a reduction in pain or no pain, tenderness, nor fever and the primary lesion area has reduced in size.
 
Else, the response will be categorized as a "Partial Response" if at the day 10-14 visit there is a reduction in pain score or no pain, tenderness, nor fever and the primary lesion area remained the same size.
 
Else, the response will be categorized as a "Failure."

Secondary Outcomes (Follow-up)	WPAI	Scores and coded variables will be derived as described in Appendix D.
Secondary Outcomes (Initial Care and Follow-up)	SF-12	SF-12 sub-scores and total scores will be compiled using the Health Outcomes Scoring Software 5.0 by QualityMetric Inc. Further detail is given in Appendix E.
Adverse Events (Baseline, Initial Care and Follow-up)	Highest severity AE	Severity of most severe AE for the patient with order of severity: Severe>Moderate>Mild Patients who only have AEs reported with missing severity,

Analysis Section (Visit)	Variable (Units)	Definition
		highest severity AE will be reported as missing

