3.3.1 Pre-period

During the pre-period, the study coordinator and/or other study nurses will identify patients who may be eligible for the study. All hospital staff may be reminded (through posters or memorandums) to inform the study coordinator and/or other study nurses as soon as an ABSSSI patient is admitted. The study coordinator will implement inclusion and exclusion criteria for the new critical pathway by patient interview and/or chart review. Inclusion criteria includes clinical judgment that patient requires coverage for a known or suspected Gram-positive infection. Patients who meet all inclusion criteria and none of the exclusion criteria based on study coordinator assessment will be enrolled in the study or flagged for further review by core study team physicians, who will make the final enrollment decision. The treating physician will be blinded to protocol content and study enrollment decision. Study coordinator will then complete all additional elements of enrollment, including informed consent, and scheduling of follow-up.

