4.1.2 Primary and secondary outcomes

Primary and secondary outcomes are presented in in Table 3. Outcomes will be assessed during initial care (the date of enrollment to 10-14 days) and follow-up (30 days after initial care) unless otherwise specified.

Table 3. Primary and secondary outcomes

Measure	Description
Infection-related total admitted hospital days during initial care and follow up	Includes days during the initial hospitalization and all other hospitalizations
Total admitted hospital days during initial care and follow up	Includes days during the initial hospitalization and all other infection-related hospitalizations
	Number of major unexpected surgeries
	Number of major expected surgeries

Measure	Description
Infection-related major surgical interventions that required operating room time during initial care and follow up	Number of all major surgical interventions unexpected or expected
Infection-related hospitalizations during initial care and follow up	Number of infection-related hospitalizations
Infection-related hospitalizations during initial care and follow-up that resulted in admission to Intensive Care Unit (ICU)	Number of infection-related hospitalizations resulting in admission to the ICU.
All cause hospitalizations in the 30 days post discharge from the hospital	Number of all hospitalizations for subjects including re-hospitalizations
Infection-related ED visits during initial care and follow up	Number of unexpected visits to ED
	Number of expected visits to ED
	All visits (unexpected and expected) to ED
Infection-related outpatient healthcare visits (e.g., physicians' office visits, ED visits, infusion center visits, home health visits) during initial care and follow up	Unexpected visits, by site (e.g., physicians' office visits, ED visits, infusion center visits, home health visits)
	Expected visits, by site (e.g., physicians' office visits, ED visits, infusion center visits, home health visits)
	All visits (unexpected and expected), by site (e.g., physicians' office visits, ED visits, infusion center visits, home health visits)
Use of PICC line or central line to administer antibiotic therapy during initial care and follow up	PICC line or central line placement for antibiotic therapy

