4.2 Primary Outcome

The primary outcome (i.e., infection-related total number of days spent in hospital) will be assessed during the 44-day period of interest, including the initial-care period (i.e., beginning on the date of enrollment and ending 14 days thereafter) and the follow-up period (the 30-day period following initial care).

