4.3 Secondary Outcomes

Secondary outcomes will be assessed during initial care (the date of enrollment to day 14) and/or follow-up (30 days after initial care), and include:

[figure not shown]
[figure not shown]
Measure	Definition	Period of Assessment
Total admitted hospital days	Total length of stay (LOS) of all hospitalizations during the 44 days of the study (including initial hospitalization)	Initial care and follow-up
Infection-related major surgical interventions that required operating room time	Number of all, unexpected and expected infection-related major surgical interventions that required operating room time	Initial care and follow-up
Infection-related hospitalizations	Number of infection-related hospitalizations	Initial care and follow-up
Infection-related hospitalizations that resulted in admission to ICU	Number of infection-related hospitalizations resulting in admission to the ICU.	Initial care and follow-up
All-cause hospitalizations in the 30 days following discharge from the initial hospitalization	Number of all hospitalizations for patients after initial hospitalization discharge	Overall, including Initial care and follow-up
Infection-related ED visits	Number of all, unexpected and expected infection-related ED visits	Initial care and follow-up

[figure not shown]
Measure	Definition	Period of Assessment
Infection-related outpatient healthcare visits (e.g., physicians' office visits, ED visits, infusion center visits, home health visits)	Number of all, unexpected and expected infection-related outpatient healthcare visits, generated for all patients and repeated by site.	Initial care and follow-up
Use of PICC line or central line to administer antibiotic therapy	Number of PICC line or central line placement for antibiotic therapy	Initial care and follow-up
Infection-related healthcare visits (e.g., hospitalizations, ED visits, other outpatient visits) due to PICC line or central line used to administer antibiotic therapy	Number of all, unexpected and expected infection-related healthcare visits due to PICC line or central line used to administer antibiotic therapy	Initial care and follow-up
Response to treatment at end of therapy visit	Response to treatment will be defined through an assessment of erythema and the absence of fever at 10-14 days and will be categorized as a complete response, partial response, or failure.	Initial care

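### The Appendix B length-of-stay formula does not match the stated 44-day outcome window: its start conflicts with other sections, it has no cap at the window's end, and it treats stays cut at discontinuation as complete

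*SAP*

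**What the plan says.** **Window.** Protocol 4.1.2 states: "Outcomes will be assessed during initial care (the date of enrollment to 10-14 days", followed by 30 more days. SAP 4.2 describes initial care as "beginning on the date of enrollment and ending 14 days thereafter", again followed by 30 days, and calls the whole a 44-day period. Appendix B defines enrollment as the date of informed consent. It codes initial care as enrollment to enrollment + 13 and follow-up as enrollment + 14 to "enrollment date + 43 days then = Yes". Protocol 3.3.3 has follow-up conclude 44 days after enrollment, which can be read as + 44.

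**Formula.** The length-of-stay row in Appendix B sums, over stays, the end date minus "Hospitalization start date +1), when both dates are available". Its only end rule is: "If ongoing at end of study or discontinuation date, use study completion date or discontinuation date as end date". The infection-related version is a subset of the same quantity. The row refers to neither period indicator.

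**Start.** Appendix B lists a separate baseline date, "Hospital admission date at initial episode of care". Under Protocol 3.3.1, staff notify the coordinator "as soon as an ABSSSI patient is admitted", and screening and consent follow. Protocol Table 3 includes the initial hospitalization in the primary outcome. For total hospital days, SAP 4.3 refers to all "hospitalizations during the 44 days of the study (including initial hospitalization").

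**Completion.** Protocol 4.2.1 plans the final contact at day 44 and allows the call up to day 51. It also plans chart review at day 44.

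**The concern.** Followed literally, the row can give a primary endpoint value that the stated window would not give. There are three routes.

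- **Start.** Days between admission and consent count in the stay but fall in neither the initial-care nor the follow-up indicator. SAP 6.2.4.1 reports initial care, follow-up and overall, so the two parts need not add up to the whole. The sections disagree on whether those days belong in the endpoint.
- **End.** A stay ongoing at study completion runs to the completion date, which may fall after enrollment + 43. A stay that ends in discharge after that day has no cap at all.
- **Discontinuation.** A stay cut off by early discontinuation is only a lower bound, yet it enters the t-test as a finished stay. The completers repeat in SAP 6.2.4.1 covers the descriptive statistics and the adjusted model. It drops these patients and recovers none of their days.

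The comparison is not randomized and the two periods enroll differently. In the pre-period the coordinator enrolls, or core-team physicians decide, with the treating physician blinded. In the post-period the coordinator or treating physician enrolls. A lag that differs between periods is therefore possible, and the visible plan has no table that would show it.

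**Working it through.** **Inputs.** From Protocol 6.3 and SAP 6.1.2: mean stay 4.0 days, SD 3.0, reduction 2.0, two-sided 0.05, 80% power, 37 per period raised to 43 for attrition. From Appendix B: window day 0 (consent) to day 43. From Protocol 4.2.1: final contact day 44, call up to day 51. The documents give no admission-to-consent lag and no attrition rate. Lag differences of 0, 0.25 and 0.5 day are assumed, and 43 − 37 = 6 is taken as the attrition allowance per period.

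**1. The plan's own figure.** Noncentral-t power for a 2.0-day difference is 79.7% at 36 per period and 80.8% at 37, so 37 reproduces. At 43 it is 86.3%. Nothing below changes the sample size.

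**2. Day counts.** With consent on day 0, the formula is F = end − start + 1. The window count is W = max(0, min(end, 43) − max(start, 0) + 1).

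| Patient | F | Comparison |
|---|---|---|
| Admitted day −1, discharged day 2 | 2 − (−1) + 1 = 4 | W = 2 − 0 + 1 = 3 |
| Readmitted day 40, still in, completion day 44 | 44 − 40 + 1 = 5 | W = 43 − 40 + 1 = 4 |
| Same, completion day 51 | 51 − 40 + 1 = 12 | W = 4 |
| Stay day 0 to 5, discontinued day 1 | 1 − 0 + 1 = 2 | actual stay = 6 |

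The first row is wrong only if the count should start at consent. The others do not depend on that choice.

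**3. Lag that differs between periods.** Equal lags cancel in the mean difference. A difference of d days (25 or 50 percentage points more patients consented one calendar day after admission in one period) shifts the estimate by d. With SD 3.0 and 43 per period the noncentrality is d / (3.0 × √(2/43)) on 84 degrees of freedom.

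- If no effect means equal post-consent days, the admission-based count rejects 6.7% of the time at d = 0.25 and 11.9% at d = 0.5. Simulation with right-skewed gamma stays (mean 4, SD 3, 40,000 trials) gives 6.6% and 12.1%.
- If no effect means equal whole stays, the admission-based count stays at 5.0%, and the consent-clipped count rejects 6.5% and 11.7% in the same kind of simulation.
- With a true 2.0-day effect, a shift of 0.25 gives power 76.2% or 93.0% depending on direction, and 0.5 gives 63.0% or 96.9%.

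**4. End overrun.** A patient in hospital throughout adds 44 − 43 = 1 day, or 51 − 43 = 8 days if a day-51 call sets the completion date. On a mean of 43 patients that is 1/43 = 0.02 or 8/43 = 0.19 day per such patient.

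**5. Truncation.** Suppose k of 43 discontinue, evenly over 44 days, each with one stay of length L from enrollment. The chance of being cut in hospital is L/44 and the mean loss is then L/2, so the mean falls by (k/43) × (mean² + SD²) / (2 × 44). For k = 6:

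- pre-period: (6/43/44) × (16 + 9)/2 = 0.003171 × 12.5 = 0.040 day;
- post-period (mean 2, SD 3): 0.003171 × (4 + 9)/2 = 0.021 day.

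The planned 2.0-day difference becomes 1.960 (pre-period only), 1.981 (both) or 2.021 (post-period only). Power is 85.0%, 85.7% or 87.0%, against 86.3%. The expected number of cut stays is 6 × 4/44 = 0.55 pre-period and 6 × 2/44 = 0.27 post-period.

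**The case against.** The strongest objection concerns the start. Protocol Table 3 and SAP 4.3 include the initial hospitalization, and the trial was sized on average hospital stay. Counting from admission is a natural reading of all three. On that reading the formula's start is right, and clipping at consent would bring enrollment timing into the endpoint. This stands. A reader might infer that the formula measures the wrong thing and that the consent-clipped count is the correct primary. The documents do not support that, because they conflict on the start.

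A reader might also infer that the pre-post comparison is biased. The documents give no lag, Protocol 3.3.3 anticipates enrollment on the day treatment starts, and equal lags cancel. A difference between periods is possible but not shown.

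On the end, few patients with a planned mean stay of 4 days will be in hospital at day 43. If the window closes at + 44, a day-44 completion is not an overrun, and no section says that a late call sets the completion date for an inpatient. All of this limits the size. It does not supply the missing cap.

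On truncation, the SAP itself notes that early discontinuation can influence length of stay and adds the completers repeat. Post-period patients without dalbavancin are outside the full analysis set, and data from patients who withdraw consent are removed (Protocol 8.3). A larger shift of 6/43 × 0.75 × 4.0 = 0.42 day can be constructed, but it needs all six to be cut off in hospital in the pre-period with 75% of the stay lost. That is a bound and should not be read as an expectation.

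Finally, the indicators could be applied day by day in programming, and the table shells, which are a separate document, may say so. The length-of-stay row does not.

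**Conclusion.** The mismatch is in the text and should be fixed. The row has no cap at the window's end, it records a cut-off stay as complete, and the sections disagree on whether counting starts at admission or consent.

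The practical effect is probably small. Truncation is expected to move a period mean by at most about 0.04 day, if up to 6 of 43 are lost evenly over the window. The overrun touches only patients in hospital at about day 43. The start matters only if the lag differs between periods; at an assumed 0.25 or 0.5 day, rejection under no effect is about 7% or 12%. That inflation falls on the admission-based count when post-consent days are equal, and on the consent-clipped count when whole stays are equal. Neither start should be presented as free of bias.

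**What to change.** 1. Cap every stay at the window's end, enrollment + 43, and reconcile that day with the wording in Protocol 3.3.3 and SAP 4.2 that can be read as + 44.
2. For discontinued patients who have withdrawn neither participation nor consent, replace the discontinuation-date rule with actual discharge and readmission dates from the planned day-44 chart review, capped at the window's end. Where these cannot be obtained, flag the stay as censored and treat it as censored in a sensitivity analysis.
3. State before analysis whether the primary count starts at admission or at consent. Make Protocol 4.1.2 (with Table 3), SAP 4.2, SAP 4.3 and the Appendix B indicators and length-of-stay row agree. Report the other start as a sensitivity analysis and tabulate admission-to-consent days by period.

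The cost is revised derivation wording, a little programming, one extra table, and chart review for a few early discontinuers at a time point already planned. The sample size does not change.
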